9.4.2.3 Subgroup Analysis

Subgroup analyses will be conducted, estimating primary and secondary endpoints (ORR, PFS, OS) in the following subgroups (but not limited to):

- Resistance to prior IO treatment (primary / early relapse on adjuvant versus acquired)
- Baseline LDH (<= ULN versus > ULN)
- Resistance to prior IO treatment (primary versus early relapse on adjuvant versus acquired)
- Baseline LDH CCI
- Sex (male versus female)
- Age at randomisation (< 65 years versus >= 65 years of age)
- Melanoma subtype (cutaneous versus acral versus mucosal)
- Presence of liver metastases (yes vs no)
- Presence of brain metastases (yes vs no)

Other baseline variables may also be assessed if there is clinical justification or an imbalance is observed between the treatment groups. The purpose of the subgroup analyses is to assess the consistency of treatment effect across expected prognostic and/or predictive factors.

The subgroup analyses for the stratification factors will be based on the values entered into the IWRS; all other factors will be based on the values recorded on the eCRF, or from the third-party vendor data.

Additional subgroups of interest and analysis methods will be outlined in the SAP.

9.4.2.4 Exploratory Endpoint(s)

Planned analysis of exploratory endpoints will be detailed in the SAP.

9.4.3 Safety

All safety analyses will be performed on the safety analysis set. Safety and tolerability will be assessed in terms of AEs (including SAEs), deaths, laboratory data, vital signs, and ECOG. These will be collected for all patients. Appropriate summaries of these data will be presented.

In general, the baseline values for statistical analysis is the last non-missing value prior to administration of the first dose of study treatment. Details are described in the SAP.

9.4.3.1 Adverse Events

AEs will be listed individually by patient and treatment group. For patients who undergo a dose modification, all AEs (due to drug or otherwise) will be assigned to the initial dose group.

Medical Dictionary for Regulatory Activities will be used to code AEs. Adverse events will be graded according to the National Cancer Institute CTCAE (Version 5.0). The number of patients in each treatment arm experiencing each AE will be summarised by MedDRA system organ class and preferred term. The number and percentage of patients with AEs in different categories (eg, causally related, CTCAE Grade \geq 3, etc) will be summarised by treatment arm; events in each category will be further summarised by MedDRA system organ class and preferred term. Serious adverse events will be summarised separately, if a sufficient number occurs.

Adverse event summary tables will include only treatment-emergent AEs. Adverse Events will be defined as treatment-emergent if they onset or worsen (by investigator report of a change in intensity), during the study treatment or safety follow-up period (defined as 30 days after last dose of study treatment) but prior to subsequent cancer therapy. AEs outside this period will only be listed.

During the evaluation of the AE data, an AstraZeneca medically qualified expert will review the list of AEs that were not reported as SAEs and AEs leading to discontinuation. Based on the expert's judgement, significant AEs of particular clinical importance may, after consultation with the Global Patient Safety Physician, be considered OAEs and reported as such in the clinical study report. A similar review of laboratory/vital signs (pulse and blood pressure) will be performed for identification of OAEs. Examples of these could be marked haematological and other laboratory abnormalities, and certain events that lead to treatment (other than those already classified as serious), dose reduction, or significant additional treatment.

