7.1.2 Follow-up of Patients Post Discontinuation of Study Treatment

After study treatment discontinuation, all patients will be followed up for safety assessments 30 days after their last dose of study treatment for ceralasertib monotherapy or 180 days after last dose of study treatment for ceralasertib and durvalumab combination (ie, the safety follow-up visit). Patients will also be followed for survival status and post discontinuation anti-cancer therapies. Additional assessments to be performed at the time of the safety follow-up are detailed in the SoA (Section 1.3). For country-specific requirements for Belgium and France see Appendices K 1.1 and K 1.2, respectively.

Patients who have discontinued study treatment prior to objective RECIST 1.1-defined radiological progression will be followed up with tumour assessments according to the SoA until RECIST 1.1 defined disease progression or death regardless of whether or not the patient started a subsequent anti-cancer therapy, unless they have withdrawn all consent to study related assessments.

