8.3.1 Time Period and Frequency for Collecting AE and SAE Information

Adverse events and SAEs will be collected from time of signature of ICF, throughout the treatment period and including the safety follow-up period (30 days after last dose of study treatment for ceralasertib monotherapy or 90 days after last dose of study treatment for ceralasertib and durvalumab combination).

If the investigator becomes aware of an SAE with a suspected causal relationship to the study treatment that occurs after the end of the clinical study in a patient treated by him or her, the investigator shall, without undue delay, report the SAE to the sponsor as described in Section 8.3.12.

For patients continuing in the PTAP, AEs and SAEs will be recorded by the treating physician from the time the participant signs informed consent and will continue throughout the program until the end of the PTAP or until consent has been withdrawn. Collection and reporting of AEs and SAEs after the final DCO is described in Section 8.3.11.

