8.3.10 Adverse Events of Special Interest

Adverse events of special interests are events of scientific and medical interest specific to the further understanding of durvalumab and ceralasertib safety profile and require close monitoring and rapid communication by the investigators to AstraZeneca. An AESI can be serious or non-serious. All AESIs will be recorded in the eCRF. Serious AESIs will be recorded and reported as per Section 8.3.12.

AESIs for durvalumab

Adverse events of special interest for durvalumab include but are not limited to events with a potential inflammatory or immune-mediated mechanism and which may require more frequent monitoring and/or interventions such as steroids, immunosuppressants and/or hormone replacement therapy. An immune-mediated AE is defined as an AESI that is associated with drug exposure and is consistent with an immune-mediated MoA and where there is no clear alternate aetiology.

If the investigator has any questions in regard to an event being an immune-mediated AE, the investigator should promptly contact the AstraZeneca clinical lead.

Adverse events of special interest/immune-mediated AE observed with anti-PD-(L)1/PD-1 agents such as durvalumab include pneumonitis, hepatitis, diarrhoea/colitis, intestinal perforation, endocrinopathies (hypo- and hyperthyroidism, adrenal insufficiency, hypophysitis/hypopituitarism and Type 1 diabetes mellitus), nephritis, rash/dermatitis, myocarditis, myositis/polymyositis, pancreatitis and rare/less frequent events (including, but

not limited to haematological events, neuromuscular toxicities [such as myasthenia gravis and Guillain-Barré syndrome], non-infectious encephalitis, non-infectious meningitis, pericarditis, rheumatological events, sarcoidosis, skin events, uveitis [and other events involving the eye] and vasculitis).

In addition, infusion-related reactions and hypersensitivity/anaphylactic reactions with a different underlying pharmacological aetiology are also considered AESIs.

More detailed guidelines for their evaluation and treatment are described in detail in the Dose Modification and Toxicity Management Guidelines (see the Annex document to this CSP). These guidelines have been prepared by the sponsor to assist the investigator in the exercise of his/her clinical judgement in treating these types of toxicities. These guidelines apply to AEs considered causally related to the study treatment/study regimen by the reporting investigator.

AESIs for ceralasertib

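### AE summary tables use a 30-day post-treatment window in both arms, although AEs and SAEs are collected for 90 days after the combination

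*Protocol*

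**What the plan says.** Protocol Section 9.4.3.1 sets three linked rules.

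- Content of the tables: "Adverse event summary tables will include only treatment-emergent AEs".
- Window: an event qualifies if it starts or worsens "during the study treatment or safety follow-up period (defined as 30 days after last dose of study treatment) but prior to subsequent cancer therapy". No arm is named, so 30 days applies to everyone.
- Remainder: "AEs outside this period will only be listed".

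Section 8.3.1 says how long AEs and SAEs are collected. It also calls this the safety follow-up period, but gives it two lengths: "30 days after last dose of study treatment for ceralasertib monotherapy or 90 days after last dose of study treatment for ceralasertib and durvalumab combination".

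The Schedule of Activities fits an arm-specific follow-up. The combination arm and the biopsy sub-study have safety visits at 30, 60, 90 and 180 days after last dose; the monotherapy arm has one at 30 days.

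**The concern.** One term has two lengths for the combination, and the analysis section uses the shorter. Collection and tabulation match for monotherapy and do not match for the combination.

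Safety and tolerability is a stated objective, and its measures include the frequency, grade and seriousness of AEs. The protocol expects durvalumab to bring a particular class of risk: its AESIs "include but are not limited to events with a potential inflammatory or immune-mediated mechanism", while Section 8.3.10 defines none for ceralasertib. The mismatch therefore falls on the treatment for which the protocol chose longer AE collection. The biopsy sub-study, which gives the combination from Cycle 1, is affected in the same way.

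At stake are the AE and SAE incidences that the study report will show for the combination. A reader of those tables would not know that 60 further days of collected events had been set aside.

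**Working it through.** The plan states no figure for this point, so there is none to reproduce. The inputs are the two windows, counted in days after last dose.

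| | Monotherapy | Combination |
|---|---|---|
| AE/SAE collection (8.3.1) | 30 | 90 |
| Eligible for summary tables (9.4.3.1) | 30 | 30 |
| Collected but not tabulated | 30 − 30 = 0 | 90 − 30 = 60 |
| Share of post-treatment collection days | 0/30 = 0% | 60/90 = 66.7% |

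**Direction of the effect.** The safety analysis set, and so the denominator, is the same whichever window is used. Every patient with a treatment-emergent event under a 30-day window also has one under a 90-day window. Combination-arm incidence under the 30-day rule is therefore lower than or equal to incidence over the collection period, never higher. Monotherapy incidence does not change.

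**Which events are affected.** Only those meeting all of these conditions:

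1. the patient's last dose was of the combination regimen;
2. the event starts or worsens on days 31 to 90;
3. no subsequent cancer therapy has begun, since 9.4.3.1 cuts there in any case.

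**Size in patients.** This would need the rate of new or worsening events after day 30, and the share of patients still alive and without new therapy between days 31 and 90. The protocol gives neither, so no count is offered. The 66.7% is a share of calendar days, not of events or patients.

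**After the change.** With 30 and 90 days used for both collection and tabulation, the gap is 0 in each arm. Post-treatment observation is then unequal: 90/30 = 3 times as many days for the combination.

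**The case against.** The strongest objection is that a common window is the fair one for comparing arms. With 90 days against 30, the combination has three times the post-treatment days in which to accumulate events, and the difference between arms could be inflated. This stands. It is the reason to keep a 30-day overview, but not a reason to make 30 days the only tabulation of the combination's own safety profile.

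A second objection is that nothing is lost: late AEs are listed by patient, deaths are listed for all patients (9.4.3.2), and an expert review may lead some events to "be considered OAEs and reported as such in the clinical study report". This is true, but listings give no incidence. The expert review is discretionary and looks at AEs other than SAEs and those leading to discontinuation, so it does not bring late SAEs into the tables.

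A third objection is that the detail belongs in the SAP. The SAP is not at hand and may define the window differently. The protocol, however, fixes the 30 days and the listing-only rule itself, and these conflict with its own collection section.

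A reader might also infer more than the text supports:

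- *All late immune-mediated toxicity disappears from the tables.* It does not. Treatment has no maximum duration, and events that start or worsen on treatment or by day 30 stay in.
- *AESI rates are understated.* Section 9.4.3.1 specifies no AESI table. Whether one would inherit this window is not stated.
- *The gap is really 150 of 180 days.* Sections 1.1 and 7.1.2 do place combination safety follow-up at 180 days, but they concern safety assessments, while 8.3.1 governs AE collection. The two can coexist. The 90-day wording for Belgium and France is country-specific text on the same safety assessments and is not in itself an error.

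**Conclusion.** The contradiction between 9.4.3.1 and 8.3.1 is real, and no other section resolves it. If 9.4.3.1 is followed as written, combination-arm AEs and SAEs that start or worsen on days 31 to 90, before subsequent cancer therapy, are collected but not tabulated: 60 of 90 post-treatment collection days, against 0 of 30 for monotherapy. Combination-arm incidence can be understated and cannot be overstated by this rule. The 60-day gap needs no assumption beyond reading both sections literally.

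The size in patients is unknown. Multiplying an assumed monthly rate by 100 patients and two months would be tempting, but no late-event rate is given, and such a product would ignore deaths and the cut at subsequent therapy. Nor does it follow that the comparison between arms is biased, because equal windows are defensible for that purpose. The primary endpoint, ORR by BICR, is untouched.

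**What to change.** - In Section 9.4.3.1, define treatment-emergent with the arm-specific AE collection period of 8.3.1: 30 days after last dose for monotherapy and 90 days for the combination, in each case before subsequent cancer therapy. Use this for the main AE and SAE tables, including those of the biopsy sub-study.
- Keep one overview table with a common 30-day window for the between-arm comparison, and say in a footnote why both are shown.
- Separately, state how the 180-day safety follow-up in Sections 1.1 and 7.1.2 relates to the 90-day AE collection period in 8.3.1.

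The cost is one changed sentence, one extra table and a clarifying line. The data are already due to be collected. The sponsor's downside is that combination-arm rates may look slightly less favourable.

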9.4.3.2 Other Safety Endpoint(s)

[figure not shown]
Clinical chemistry, haematology, urinalysis, and vital signs will be listed individually by patient and appropriately summarised. For all laboratory variables that are included in the CTCAE (version 5.0), the CTCAE grade will be calculated.

Details of any death will be listed for all patients.

9.4.4 Other Analyses

Biopsy sub-study: CD8+ T-cells tumour infiltration and other biomarkers measured in tumour and periphery will be summarised descriptively in baseline, ceralasertib on-treatment and ceralasertib off-treatment samples, and longitudinal blood samples. Data will be transformed as appropriate eg, log₂-transformation, and analysed by MMRM with fixed effect for timepoint. An unstructured variance-covariance matrix will be used to accommodate repeated measures within a patient, assuming model convergence otherwise alternatives will be used as detailed in the SAP. The least square means for each timepoint will be presented, together with the difference to baseline visit and 95% confidence interval.

Association of biomarkers to clinical outcomes will be presented visually, eg, boxplots by BOR.

9.5 Interim Analyses

analyses of efficacy data will be conducted during the study.

The CCI analysis will be once approximately patients have been enrolled (approximately patients in the ceralasertib and durvalumab combination therapy arm and approximately patients in the ceralasertib monotherapy arm) and had the opportunity for approximately weeks follow up. The weeks follow up enables RECIST scans for confirmation of response. The rationale for this approach is to ensure the ORR is not artificially underestimated at an interim analysis eg, if there are patients ongoing treatment with unconfirmed response who are yet to have their confirmatory scan.

The IDMC may recommend to stop recruitment to the ceralasertib plus durvalumab treatment arm if there are or occur responses out of patients, ie, $ORR \le 0\%$. This stop rule corresponds to < 0% predictive probability of success should recruitment continue to the end of the study. There is % risk to incorrectly stop if the true ORR = 0%.

The IDMC may recommend to stop recruitment to the ceralasertib monotherapy arm if there are responses out of patients ie, ORR=1%. The stop rule for the monotherapy arm is more conservative, intended to mitigate risk of harm relative to other treatment options for patients eg, chemotherapy, but otherwise continuing recruitment in order to have adequate precision in the comparison to the ceralasertib plus durvalumab arm to characterise the contribution of components at study end. Should the combination treatment arm be terminated at the interim analysis, the monotherapy arm may also be terminated if there are or ceralasertib patients, ie, $ORR \le 1\%$ since in this situation it is unlikely to achieve the target ORR to warrant future development should it continue to the end of the study.

analysis will be once approximately patients have been enrolled (approximately patients in the ceralasertib and durvalumab combination therapy arm and approximately patients in the ceralasertib monotherapy arm) and had the opportunity for approximately weeks follow up. The weeks follow up enables RECIST scans for confirmation of response and also preliminary characterisation of the durability of response, which is a key secondary endpoint. The IDMC may recommend to stop recruitment to combination treatment arm if there are fewer responses out of patients, ie, ORR size or responses out of patients ie, ORR size of which is a comparison of patients with non-progressive disease at weeks is size of which is a comparison of patients with non-progressive disease at weeks is size of which is a comparison of patients with non-progressive disease at weeks is size of which is a comparison of patients with non-progressive disease at weeks is size of which is a comparison of patients with non-progressive disease at weeks is size of which is a comparison of patients with non-progressive disease at weeks is size of which is a comparison of patients with non-progressive disease at weeks is size of which is a comparison of patients with non-progressive disease at weeks is size of which is a comparison of patients in the ceralasertib and durvalumab combination therapy arm and durvalumab combination therapy arm and approximately particles are not provided in the ceralasertib and durvalumab combination therapy arm and durvalumab combination therapy arm and approximately particles are not provided in the ceralasertib and durvalumab combination therapy arm and durvalumab combination therapy arm and approximately particles are not provided in the ceralasertib particles are not provided in the ceralasert

Should the combination treatment arm be terminated at the interim analysis, the monotherapy arm may also be terminated if there are or fewer responses out of patients, ie, ORR \leq in this situation it is unlikely to achieve the target ORR to warrant future development should it continue to the end of the study. In addition,

ORR will be evaluated by BICR at interim analyses. The IDMC will review all available safety and efficacy data at each interim analysis and any recommendation to stop recruitment to a treatment arm will be based on review of the totality of data across the study. Recruitment will not be paused during the conduct of the interim analyses. Full details on the content of safety and efficacy data reviews will be documented in the IDMC charter.

The SAP will describe the planned interim analyses in greater detail.

In addition, the number of patients with primary IO resistance, early relapse on adjuvant therapy or acquired IO resistance will be monitored throughout the study, and enrolment may be capped to any group at any time to ensure a minimum of approximately % of patients with primary and approximately % of patients with secondary resistance.

9.6 Independent Data Monitoring Committee

An IDMC comprised of independent experts will be convened and will meet for a safety review approximately when patients in the ceralasertib and durvalumab combination therapy arm and patients in the ceralasertib monotherapy arm achieve 1 cycle (4 weeks) worth of data. The IDMC will convene to review the unblinded safety and tolerability data and the unblinded efficacy data from the interim analyses, in order to recommend to the sponsor to continue, amend, or stop the study based on the safety and efficacy findings. The committee will meet approximately every 3 months thereafter. The IDMC would also perform the interim analysis at the timepoints detailed in Section 9.5.

This committee will be composed of a minimum of 3 therapeutic area experts and biostatisticians, who are not employed by the sponsor and are free from conflict of interest. The precise timings of the initial IDMC meeting and subsequent meetings will be specified in the IDMC Charter. The IDMC Charter will be approved prior to the first IDMC Data Review meeting.

Following the reviews, the IDMC will recommend whether the study should continue unchanged, be stopped, or be modified in any way. Once the IDMC has reached a recommendation, a report will be provided to an unblinded review committee at the sponsor. The report will include the recommendation and any potential CSP amendments. The final decision to modify or stop the study will sit with the sponsor. The sponsor or IDMC may call additional meetings if at any time there is a concern about the safety of the study.

Full details of the IDMC procedures, processes, and interim analyses can be found in the IDMC charter.

For details on IDMC, refer to Appendix A 5.

10 SUPPORTING DOCUMENTATION AND OPERATIONAL CONSIDERATIONS

Appendix A Regulatory, Ethical, and Study Oversight Considerations

A 1 Regulatory and Ethical Considerations

- This study will be conducted in accordance with the protocol and with the following:
 - Consensus ethical principles derived from international guidelines including the Declaration of Helsinki and Council for International Organizations of Medical Sciences (CIOMS) International Ethical Guidelines
 - Applicable ICH GCP Guidelines
 - Applicable laws and regulations
- The protocol, protocol amendments, ICF, Investigator's Brochure, and other relevant documents (eg, advertisements) must be submitted to an IRB/IEC by the investigator and reviewed and approved by the IRB/IEC before the study is initiated.
- Any amendments to the protocol will require IRB/IEC and applicable Regulatory Authority approval before implementation of changes made to the study design, except for changes necessary to eliminate an immediate hazard to study patients.
- AstraZeneca will be responsible for obtaining the required authorisations to conduct the study from the concerned Regulatory Authority. This responsibility may be delegated to a CRO but the accountability remains with AstraZeneca.
- The investigator will be responsible for providing oversight of the conduct of the study at the site and adherence to requirements of 21 CFR, ICH guidelines, the IRB/IEC, European Regulation 536/2014 for clinical studies (if applicable), European Medical Device Regulation 2017/745 for clinical device research (if applicable), and all other applicable local regulations.

Regulatory Reporting Requirements for SAEs

- Prompt notification by the investigator to the sponsor of a SAE is essential so that legal obligations and ethical responsibilities towards the safety of patients and the safety of a study treatment under clinical investigation are met.
- The sponsor has a legal responsibility to notify both the local regulatory authority and other regulatory agencies about the safety of a study treatment under clinical investigation. The sponsor will comply with country-specific regulatory requirements relating to safety reporting to the regulatory authority, IRB/IEC, and investigators.
- In the European Union, the Sponsor will comply with safety reporting requirements and procedures as described in the European Clinical Trials Regulation (EU) No 536/2014.

All SUSARs to investigational medicinal product will be reported to the EudraVigilance database within the required regulatory timelines.

- For all studies except those utilizing medical devices investigator safety reports must be prepared for SUSARs according to local regulatory requirements and sponsor policy and forwarded to investigators as necessary.
 - European Medical Device Regulation 2017/745 for clinical device research (if applicable), and all other applicable local regulations
- An investigator who receives an investigator safety report describing a SAE or other specific safety information (eg, summary or listing of SAEs) from the sponsor will review and then file it along with the Investigator's Brochure and will notify the IRB/IEC, if appropriate according to local requirements.

Regulatory Reporting Requirements for Serious Breaches of Protocol or GCP

A 'Serious Breach' means any deviation of the approved version of the protocol or Good Clinical Practice (GCP) that is likely to affect the safety, rights of study patients and/or data reliability and robustness to a significant degree in a clinical trial.

All parties (Sponsor, service provider, investigator site staff) involved in the conduct of the clinical trial:

- Are responsible for promptly identifying and documenting any actual or potential serious breach.
- Should have a process in place to ensure that they are able to identify the occurrence of a (actual/potential) serious breach.
- Should report to AstraZeneca (or delegated party) without delay, through the contacts (email address or telephone number) provided by AstraZeneca.

A 2 Financial Disclosure

Investigators and sub-investigators will provide the sponsor with sufficient, accurate financial information as requested to allow the sponsor to submit complete and accurate financial certification or disclosure statements to the appropriate regulatory authorities. Investigators are responsible for providing information on financial interests during the course of the study and for 1 year after completion of the study.

A 3 Informed Consent Process

• The investigator or his/her representative will explain the nature of the study to the patient or his/her legally authorised representative and answer all questions regarding the study.

- Patients must be informed that their participation is voluntary and they are free to refuse to participate and may withdraw their consent at any time and for any reason during the study. Patients or their legally authorised representative will be required to sign a statement of informed consent that meets the requirements of 21 CFR 50, local regulations, ICH guidelines, Health Insurance Portability and Accountability Act (HIPAA) requirements, where applicable, and the IRB/IEC or study centre.
- The medical record must include a statement that written informed consent was obtained before the patient was enrolled in the study and the date the written consent was obtained. The authorised person obtaining the informed consent must also sign the ICF.
- Patients must be re-consented to the most current version of the ICF(s) during their participation in the study.
- A copy of the ICF(s) must be provided to the patient or the patient's legally authorised representative.

For country-specific requirements for Germany see Appendix K 1.3.

Patients who are rescreened are required to sign a new ICF.

The ICF will contain a separate section that addresses and documents the collection and use of any mandatory and/or optional human biological samples. The investigator or authorised designee will explain to each patient the objectives of the analysis to be done on the samples and any potential future use of the samples and the data obtained from these samples. Patients will be told that they are free to refuse to participate in any optional samples or the future use and may withdraw their consent at any time and for any reason during the retention period.

If a patient's partner becomes pregnant within 90 days after the last dose of durvalumab, the partner is asked to sign the "Adult Study Informed Consent Form for Pregnant Partners of Study Patients" and provide information about the pregnancy accordingly.

A 4 Data Protection

- Patients will be assigned a unique identifier by Trusted Third Party contracted by the Sponsor or by a Principal Investigator. Any patient records or datasets that are transferred to AstraZeneca will contain the identifier only; patient names or any information which would make the patient identifiable will not be transferred.
- The patient must be informed that their personal study-related and coded (pseudonymised) data will be used by AstraZeneca in accordance with local data protection law. The purposes of use and the level of disclosure and use of their data (including the legal basis AstraZeneca relies upon processing their data, where required) must also be explained to the patient in the informed consent.

- The patients must be informed that their medical records may be examined by Quality Assurance auditors or other authorised personnel appointed by AstraZeneca, who are independent of the staff involved in the study in accordance with current Quality Assurance Standard Operating Procedures and Quality Assurance Audit Schedule; by appropriate IRB/IEC members; and by inspectors from regulatory authorities.
- The patient must be informed that data will be collected and used to develop the drug/investigational product, get permission to introduce and keep it on the market, monitor its safety and get it reimbursed eg, by governments eg, throughout the drug development programme, which includes related research activities necessary for this drug development programme, including to: understand how the study drug(s) and similar drugs work in the body (eg, evaluate the study drug mode of action, alone or in combination with other study drugs); better understand the studied disease and associated health problems; develop diagnostic tests for the disease; learn from past studies to plan new studies or improve scientific analysis methods; publish research results in scientific journals or use them for educational purposes. AstraZeneca will only collect and use the minimum amount of personal data to support the research and safety monitoring activities within the drug development programme and will not make personal data available to anyone (including internal staff) who is not authorised or does not have a business need to know the information.
- The patient must be informed that in some cases their data may be further pseudonymised and/or anonymised.
- Appropriate safeguards will be implemented to protect coded data during and after the study that include:
 - Access to the coded data will be restricted and monitored, and limited to specific individuals subject to confidentiality obligations (including the obligation to not attempt to re-identify individuals/decode the clinical data).
 - The coded data will be protected with security measures to avoid data alteration, loss, and unauthorised accesses and further de-identification techniques may be applied; as well as other high-standard technical security means such as encryption.
 - A data protection impact assessment, where required, will apply to identify and mitigate privacy risks, if any, associated with each scientific research.
 - The coded data will not be shared for direct marketing purposes or other purposes
 that are not legal duties or are not related to scientific research purposes of the study.
 In particular, it will not be used to make decisions about future services available to
 the patient, such as insurance.
- Patients are also protected legally by the following means, if the coded data will be shared with third parties other companies within the Sponsor group; Service providers;

Research partners, who may be located in countries which do not offer the same level of protection as the patients' country for which the patient will be informed in the ICF:

- Within the Sponsor group, the patients' coded data are protected by BCR. More information about the Sponsor's BCR is provided here:
 www.astrazenecabindingcorporaterules.com, or by other contractual arrangements as may be required under local law.
- In all other cases, the patients' coded data is protected by contractual arrangements,
 Codes of Conduct, or certifications that set the rules for personal data protection to
 those available in the patient's country or other alternatives set forth in the law, as
 well as any supplementary technical and organisational measures that may results out
 of conducted transfer impact assessments, where required.

Personal Data Breaches

A 'personal data breach' means a breach of security leading to the accidental or unlawful destruction, loss, alteration, unauthorised disclosure of, or access to, personal data transmitted, stored or otherwise processed.

- In compliance with applicable laws, the Data Controller¹ for the processing activity where the personal data breach occurred (AstraZeneca or respectively the site), will notify the data protection authorities without undue delay within the legal terms provided for such notification and within the prescribed form and content.
- Whilst AstraZeneca has processes in place to deal with personal data breaches it is important that investigators that work with AstraZeneca have controls in place to protect patient data privacy.

The Investigator should have a process in place to ensure that:

- Allow site staff or service providers delegated by the investigator/institution to identify the occurrence of a (potential) personal data breaches.
- Any (potential) personal data breach is promptly reported to AstraZeneca or delegated party, through the contacts (e-mail address or telephone number) provided by AstraZeneca.

¹ The **data controller** determines the **purposes** for which and the **means** by which personal data is processed, as defined by the European Commission

AstraZeneca and the site must demonstrate that they:

- have taken all necessary steps to avoid personal data breaches and
- have undertaken measures to prevent such breaches from occurring in the first place and to mitigate the impact of occurred data breaches (eg, applying encryption, maintaining and keeping systems and IT security measures up-to-date, regular reviews and testing, regular training of employees, and developed security policies and standards).
- where possible, have developed an internal data breach reporting and investigation process and internal protocols with guidance on how to respond swiftly and diligently to the occurrence of a personal data breach.
- where it has not been possible to develop an internal data breach reporting and investigation process, the site follows AstraZeneca's instructions.

Notification of personal Data Breach to patient:

- Notification to patient is done by the site for the data breaches that occurred within the processing activities for which the site is the Data Controller and for data breaches occurred within the processing activities of AstraZeneca as the Data Controller, the notification is done in collaboration with the site and is performed by the site and/or Principal Investigator, acting on behalf of AstraZeneca, so that AstraZeneca has no access to the identifying personal information of the patient. The site and/or Principal Investigator shall conduct the notification by contacting the patient using the information that they gave for communication purposes in clinical research.
- If a personal data breach occurs in a processor's systems, engaged by AstraZeneca, the processor under contractual obligations with AstraZeneca promptly and in due course after discovering the breach notifies AstraZeneca and provides full cooperation with the investigation. In these cases, to the extent AstraZeneca is the Data Controller for the processing activity where the breach occurred, it will be responsible for the notification to data protection authorities and, if applicable, to patient. If the personal data breach needs to be notified to the patient, the notification to patient is done in collaboration with the site and is performed by the site and/or Principal Investigator, acting on behalf of the Sponsor, so that AstraZeneca has no access to the identifying personal information of the patient.
- If a personal data breach involving an AstraZeneca's representative device (ie, Study Monitor laptop), AstraZeneca representative will provide AstraZeneca with all of the information needed for notification of the breach, without disclosing data that allows AstraZeneca directly or indirectly to identify the patient. The notification will be done by AstraZeneca solely with the information provided by the Study Monitor and in no event with access to information that could entail a risk of re-identification of the patient. If the data breach must be notified to the data subjects, the notification will be done directly by

the Study Monitor in collaboration with the site and/or Principal Investigator, acting on behalf of the Sponsor, so that AstraZeneca has no access to the identifying personal information of the patient. The contract between AstraZeneca and the Study Monitor shall expressly specify these conditions.

• The contract between the site and AstraZeneca for performing the clinical research includes the provisions and rules regarding who is responsible for coordinating and directing the actions in relation to the breaches and performing the mandatory notifications to authorities and patients, where applicable.

A 5 Committees Structure

The safety of all AstraZeneca clinical studies is closely monitored on an ongoing basis by AstraZeneca representatives in consultation with Patient Safety. Issues identified will be addressed; for instance, this could involve amendments to the CSP and letters to investigators.

A 6 Dissemination of Clinical Study Data

